#### **Potential Risks:**

**Physical:** The experimental intervention of iTBS being provided is a patterned form of rTMS. The biggest concern for transcranial magnetic stimulation (TMS) is seizure induction. Other known side effects of rTMS include headache, dizziness, tinnitus, nausea, neck pain, or scalp burns. Side effects reported to date for iTBS include sweating, feeling dizzy, neck pain, mild decrease in diastolic blood pressure, headache, discomfort/mild tingling sensation, occasional local pain or discomfort during stimulation, and isolated, transient, non-pulsatile, left-sided tinnitus. Additionally, there is risk of equipment malfunction. The Magventure MagProX100 with MagOption stimulator and Magpro Cool Coil B65 or one of the coils may malfunction which may result in harm to the patient.

Participation in the AMPS requires the Veteran to complete a variety of physical tasks that may be challenging to complete. There is a risk of injury depending on the type of task the Veteran identifies as valuable to complete (e.g. burns, laceration, falls).

**Psychological:** Participation in the study outcome measures, including self-report (i.e. PCL), observational (i.e. ABS), neuropsychological (i.e. DKEFS, WAIS-IV), cognitive capacity and function outcomes (i.e. AMPS, RBANS), effort testing (i.e. DCT) structured interview data (AMPS) and safety outcomes (Data Safety Monitoring Scale), involves minimal risks and discomforts. The risks for the Veteran include frustration, agitation, anxiety, fatigue, and possible trigger of PTSD symptoms.

**fMRI:** There are no known risks associated with fMRI when individuals are appropriately screened, except some people have experienced discomfort in trying to remain still. MRI is not safe when specific ferromagnetic materials are present in the body (i.e. metal fragments in brain/skull, metal surgical clips, etc). Some people have been noted to be anxious or claustrophobic during the scan. The MRI scanner makes loud banging noises during scanning.

**EEG:** The self-adhesive used with surface EEG electrodes may produce minor irritation of the skin. The possibility of irritation will be minimized by applying gel to the skin prior to electrode placement and by cleaning the skin with alcohol before and after the application of the electrodes. If there is irritation, then additional gel will be used on future applications. There is also the possibility of an allergic reaction to the electrode gel. If the participant is allergic to the gel, then the response plan is to use an alternative gel. If the scalp is red to the extent beyond minor irritation, then the response will be to substitute the standard EEG electrode placement with conductive plastic electrodes and the standard electrode placement will still be used.

#### **Protection Against Risk:**

**Physical:** In order to minimize the risk of harm from seizure should one occur during iTBS, motor thresholding and all treatments will be provided in a room within the hospital's Rapid Response

area. If Veterans show any signs of seizure or other adverse reaction, study team will contact the Hines Rapid Response Team via Rapid Response call button or via phone. Once the Rapid Response Team arrives, they will assume responsibility for carrying out all emergency procedures.

The treatment room is equipped with a crash cart, defibrillator, pyxis machine and all equipment needed to monitor vital signs. The Rapid Response team is triggered via phone call using the phone physically located in this room. There is also an accessible code button within 20 feet of this room. Researchers have completed training with the Rapid Response and Code teams on activating these emergency systems as well as monitoring and caring for the subject while awaiting arrival of the Rapid Response or Code teams.

To prevent hearing loss, all Veterans will wear headphones during the iTBS intervention. For Veterans who are receiving placebo iTBS, the sham noise generator will be set to a sound level that is within the normal hearing range to prevent hearing damage.

The following safety indicators will be tracked at each study day: blood pressure, heart rate, fatigue, tinnitus, sleep, dizziness, nausea, vomiting, confusion, seizure, headache, and neck pain. Change from baseline is rated according to severity and for each severity rating there is a specified medical response to be followed. The ratings are on a scale of 1 to 5 with a higher number indicating more deleterious change.

To minimize the risks of iTBS, the following rules will apply for pausing, stopping or rescheduling iTBS:

**Rules for Pausing treatment to Evaluate Need to Change iTBS Treatment Protocol:**

- 1) Any seizure
- 2) Skin break-down on scalp at site of TMS
- 3) Constant headaches that do not resolve with acetaminophen
- 4) Suicidality response on C-SSRS is 2 or higher
- 5) A composite score of visuomotor processing speed assessments that falls below 2 standard deviations from the mean.

**Rules for Stopping iTBS Treatment/Study Participation:**

- 1) Shock (of any etiology),
- 2) Any seizure activity that study epileptologist deems as categorizing someone as unsafe to continue iTBS
- 3) A participant who previously agreed during consenting procedures to stop taking amphetamine and non-amphetamine/methylphenidate CNS stimulant medications reports initiating taking these medications, and does not wish to forgo CNS stimulants for remainder of study participation
- 4) Any participant experiences a change to their prescribed medications, either initiating a new mental health medication or experiencing a prescribed change in dose for mental health reasons during study participation
- 5) Participants with a positive urine pregnancy screen or report new pregnancy (for females)

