**Study-Day 3 (2 weeks after Study Day 2)(~8 hours):**

- 1. PE testing battery
- 2. Single session **Active** iTBS+ APT or **Placebo** iTBS+APT
- 3. Alternate ImE test (MDS or AMPS) three times at 30min intervals
- 4. PE testing battery
- 5. Suitability ratings 1-3

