**Study-Day 4 (2 weeks after Study-Day 3) (~2.5 hours):**

[figure not shown]
- 1. PE testing battery
- 2. Suitability rating 1-8

**Optional Study for Participants with diagnosis of TBI only- Day 5 (to occur within 2 weeks of Day 4, can occur on same day as Day 4) (~2 hours)**

- 1. Single session of Active iTBS at GIMME site of stimulation
- 2. ImE test: MDS, one time only
- 3. ImE test: AMPS, one time only

### Figure 3. Study Procedures by Study-Days 1 thru 4

ImE = Immediate Effects Tests; s-AMPS = Streamlined AMPS or MDS = Modified Digit Span; PE = Persisting Effects Tests for all participants

**Interventions.** All iTBS sessions will be **double-blinded**, but APT exercises **will not be blinded**. For **Active** iTBS and **Placebo** iTBS, the left DLPFC using the Resting Network Mapping algorithm.

**fMRI (neuroimaging)-** Functional MRI (fMRI) measures will be collected at Baseline. The fMRI measures will include structural imaging, 20 minutes of resting-state fMRI, diffusion tensor imaging (DTI) and an Arterial Spin Labelling Sequence (ASL). Participants will be in the MRI for approximately 55 minutes. fMRI scanning, for all participants, will take place at Northwestern University's CTI in the Olsen Pavilion located at [name].

Veterans will be responsible for transportation to the CTI, however parking vouchers will be provided at no cost to the participant. Parking is available at the Northwestern Memorial Hospital parking garage located across from the Olsen Pavilion. Research staff will be present on day of scan and available to provide assistance.

Scanning will take place on a Siemens Prisma 3.0 T MRI scanner equipped with a 64-channel head/neck coil. A high-resolution 3D MP-RAGE T1-weighted sagittal anatomical scan (voxel size = 0.8 mm isotropic resolution; 224 sagittal slices) will be collected for each participant. Resting state BOLD data will be collected using T2\* weighted EPI with a TR=0.5s, TE=25ms, flip angle of 48°, and 2mm isotropic voxels and a multiband factor of 8. Rest data will be collected while the subject views a fixation crosshair. The DTI data will use a two shell (64 directions per shell) acquisition with diffusion values of 1000 mm^2/sec. The acquisition will collect 1.5mm isotropic voxels with a TR=4500, TE=62ms and a multiband factor of 4, and 96 slices.

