For Aim 3, we will compute study attrition as percent of participants dropping out after Study-Day 2 and after Study-Day 3. We will examine whether or not these attrition rates differ (3i) by stroke and TBI groups using chi-square. To examine if Veteran's with stroke and TBI have (3ii) different perceptions regarding the suitability of the number and type of tests and number of study-days, we will compare each group's average ratings, by suitability index, using t-tests. To explore the relationship between perceived suitability and fatigue as well as mood (3iii), we will compute Pearson correlations at each of the 5-timepoints (B0 through B4) between average ratings of suitability indices 1 through 3 and averages for each of the two fatigue measures and each of the five mood measures [5x (3x2) + 5x (3x5) = 105 correlations]. We will also compute correlations for average suitability indices 7 through 8 collected on Study-Day 4 (B4) with the averages from that same day for each of the two fatigue measures and each of the five mood measures [1x (2x2) + 1x (2x5) = 14 correlations]. We will test the significance of each correlation using Fisher Z test and results will be interpreted accordingly.

Aims 2 and 3 involve multiple comparisons. Bonferroni correction of type I error rate is very conservative, and, at this early research stage, it could mask important findings. Thus, we will control for false discovery rate (FDR) using an FDR level of .05.

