## 5.7 Withdrawal of Subjects

Study participants will be informed during the consent process that their participation in the study protocol is voluntary, and they may choose to discontinue research participation at any time. Discontinuation of research participation will not impact medical care received outside of the research study. Individuals may choose to withdraw from the study for medical or non-medical reasons. If withdrawal from the study occurs during the provision of iTBS, regardless of whether this withdrawal is related or unrelated to the protocol, participants will be evaluated by the study physician and a medically appropriate plan for follow up will be established in a manner that maintains the safety of the research participant. The PI may also choose to withdraw a participant from the study if by the PI's judgment continuation in the study is not in the best interest of the participant for health or safety reasons, non-compliance with study procedures or loss of funding for the project.

Every attempt will be made to retain research participants in this study. Research participants who do not complete their study participation will be replaced only if they withdraw prior to any research procedures past the baseline measures. Unless a research participant revokes his/her consent to use their health information (i.e. revocation of HIPAA Authorization), any data collected prior to study withdrawal will be used in data analysis.

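### The stopping rules do not separate ending iTBS from ending study participation, so a mental-health medication change may also end the scheduled assessments, and Aim 3 attrition does not distinguish such mandated stops from voluntary dropout

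*Combined protocol and SAP*

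**What the plan says.** Section 5.1, under Protection Against Risk, introduces three lists by saying that "the following rules will apply for pausing, stopping or rescheduling iTBS". The pausing list and the rescheduling list have headings that refer to treatment only. The stopping list alone is headed "Rules for Stopping iTBS Treatment/Study Participation".

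Rule 4 of the stopping list begins "Any participant experiences a change to their prescribed medications, either initiating a new mental health medication". Its second limb is a change of dose made on mental-health grounds, and both limbs apply throughout a Veteran's time in the study. It has no cut-off at the last stimulation session.

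The last main-study stimulation is on Study-Day 3 ("Single session Active iTBS+ APT or Placebo iTBS+APT"). The next visit is "Study-Day 4 (2 weeks after Study-Day 3") and holds only the persisting-effects (PE) battery, B4, and the suitability ratings. An optional iTBS session, for Veterans with TBI only, may follow on Day 5 or on the same day as Day 4.

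Section 5.7 promises that, unless authorisation is revoked, "any data collected prior to study withdrawal will be used in data analysis". It limits replacement to Veterans who leave before any procedure beyond baseline. Section 5.6 compares PE measures between arms with t-tests, gives no missing-data method, and defines Aim 3 attrition as the "percent of participants dropping out after Study-Day 2 and after Study-Day 3".

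**The concern.** Stopping a treatment and stopping observation are different decisions. If a medication change ends both, later outcomes are missing for a reason that may be related to what is being measured: the PE battery contains the PCL, BAI and C-SSRS, listed for Aims 2 and 3. The two-week and cumulative comparisons would then describe Veterans whose mental-health treatment stayed constant. Aim 3 attrition is meant to inform the feasibility of the next trial and is compared between stroke and TBI. It could mix removals made by the protocol with Veterans' own decisions to leave.

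**Working it through.** **1. The plan's own allowance for loss.** Inputs from section 5.6: 80% power, effect size 0.90, 12% attrition. Alpha is not stated for the sample size; two-sided 0.05 is assumed. A two-sample t-test needs 20.39 per group, so 21 per group and 42 in total. 42 / (1 - 0.12) = 47.7, so 48. The plan's 21, 42 and 48 reproduce. The allowance is 48 - 42 = 6 losses (48 x 0.12 = 5.76).

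**2. Does a stop end assessment?**
- For: only the stopping list adds study participation to its heading. The rescheduling list lets a Veteran who is willing to give up stimulants continue in the study, which implies that the unwilling Veteran in stopping rule 3 does not continue. No section provides for off-treatment assessment.
- Against: the lead-in confines all three lists to iTBS, and no sentence says that assessments cease.

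The two texts differ in scope, so staff could handle the same event differently.

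**3. What is lost on the heading's reading.**

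| Medication change occurs | Lost | Kept |
|---|---|---|
| Between Day 2 and Day 3 | B2, B3, B4 (3 of 5 PE batteries), second immediate-effects series, Day 3 and Day 4 ratings | B0, B1, first immediate-effects series |
| Between Day 3 and Day 4 | B4 (1 of 5), Day 4 ratings | B0 to B3, both immediate-effects series |

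B4 is the only two-week follow-up of iTBS + APT. Suitability items 4 to 8 are rated only on Day 4, and items 7 and 8 feed (2 x 2) + (2 x 5) = 14 planned correlations.

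**4. Link to mood.** The protocol's own safety steps can lead to the trigger. PTSD symptoms provoked by testing prompt a Mental Health Service consultation whose advice is followed, and some C-SSRS answers prompt psychiatric evaluation. If that care includes a medication change, rule 4 is met.

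**5. Size, under assumptions only.** The documents give no rate of medication change.
- Count: 48 x 0.05 = 2.4 and 48 x 0.10 = 4.8, so about 2 to 5 Veterans at an assumed 5-10%.
- Power at effect size 0.90 if the loss comes on top of planned attrition, with n = 21 x (1 - r) per group: r = 0, 5%, 10%, 20% gives n = 21, 19.95, 18.9, 16.8 and t-test power 0.81, 0.79, 0.77, 0.72.
- Shift in one group's mean if exactly the worst-mood fraction q is removed and mood correlates rho with the outcome (normal model): rho x phi(z) / (1 - q), where z is the upper-q normal point. This gives 0.02 SD (q = 5%, rho = 0.2), 0.08 SD (10%, 0.4) and 0.21 SD (20%, 0.6). Equal shifts in both arms cancel in the contrast.

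**6. Aim 3.** With 24 Veterans per diagnosis, each mandated stop counted as dropout moves that group's attrition by 1/24 = 4.2 percentage points.

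**The case against.** The strongest reply is that the lead-in governs: the rules concern iTBS, section 5.7 says every effort will be made to retain participants, and where the protocol intends exclusion (active suicidal ideation) it says so. That reply stands in part. A reader might infer several things that the documents do not support:

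- That the protocol states that assessments end. It does not; this is inferred from the heading and from the absence of any off-treatment follow-up.
- That section 5.7 discards later data. It is a promise to retain earlier data and is silent on data collected after iTBS stops without study withdrawal.
- That the rule removes Veterans whose mood worsens. It covers any dose change for mental-health reasons, including a reduction after improvement.
- That the arm contrast is biased. That requires stopping to differ between arms.
- That no stimulation is ever left after Day 3. This is true of the main study only; up to 12 Veterans with TBI may have the optional session.
- That mandated stops certainly count in Aim 3. The definition does not say either way.

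Entrants are also screened for recent medication changes, which may keep the rate low, and 2 to 5 losses would fit within the allowance of 6, though other losses share it. The immediate-effects data behind Aim 1 are untouched by a stop after Day 3.

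The reply does not remove the conflict between heading and lead-in, the missing cut-off in rule 4, or the absence of a missing-data method.

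**Conclusion.** The concern holds in a limited form. The heading and the lead-in disagree on scope, and nothing provides for assessment after iTBS is stopped. On the heading's reading, a mental-health medication change costs either three PE batteries and the second immediate-effects series, or B4 and the Day 4 ratings. The loss is plausibly related to mood and can make the B2 to B4 results unrepresentative; any arm bias depends on differential stopping. The size cannot be derived from the documents, and the rates, correlations and power figures above are illustrations resting on assumed inputs. Selection matters more than lost power: at an assumed extra 10% loss, power falls only from 0.81 to 0.77. Aim 3 attrition needs a definition that separates mandated from voluntary exits. None of this questions which events should stop iTBS.

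**What to change.** Reconcile the lead-in, the stopping list and section 5.7 by giving separate rules for stopping iTBS and for stopping study participation. Which events trigger each, and any safety-based end of participation, stay with the sponsor.

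For Veterans stopped from iTBS because of a medication change who still consent:
- keep the PE batteries already scheduled at B2 and B4, on their original dates;
- record the reason and date of the stop and the medication change;
- analyse them as randomised, with one sensitivity analysis excluding values after the medication change and, for iTBS + APT estimates, one excluding Veterans who never received that session.

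In Aim 3, report mandated stops separately from voluntary dropout, overall and by diagnosis.

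The cost is protocol wording, a small addition to the case-report form and two short sensitivity analyses; the visits are already in the schedule. The downside is small: some later values will follow a medication change or a missed session, which the sensitivity analyses address.

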***Screening Medical Records:***

The VA electronic medical record and any non-VA medical records will be reviewed to confirm completion of rehabilitation services as indicated by inpatient/outpatient therapy reports and notes. Veterans actively receiving therapy services will be excluded. To examine medical stability, we will also confirm that medical status has remained stable for three months (e.g., new seizures, new diagnoses) prior to the records review as well as absence of other exclusionary conditions (e.g., having both TBI and ischemic stroke). We will also review medications to identify Veterans actively receiving pharmacological neurostimulants. These cases will be reviewed by the study neurologist who will consult with the prescribing physician to determine safe withdrawal, via titration. If there is question about safety, then the Veteran will be

excluded. Dictated radiology reports will be reviewed to identify Veterans with ischemic strokes bilaterally who will be excluded.

**Medication Review:** For participant inclusion and safety, if the participant is prescribed medication known to act on the CNS, an evaluation of cumulative seizure risk and appropriate risk mitigation for each patient according to their prescribed medication profile and relative to self-reported medications, alcohol consumption (AUDIT-C) and substance use (DAST-10) will be evaluated prior to enrollment. In lieu of excluding participants based on the name of any particular drugs or drug classes or limit them to a set, we will follow the procedure as described:

- Clinical experts (e.g., Research Neuropsychiatrist [name], Neuropsychologist [name], Neurologist and Epileptologist [name], Neurologist and Stroke Expert [name]) and/or scientific subject matter experts (e.g., TBI expert [name], AUD and SUD expert [name]) will review all CNS acting medications for each research candidate/participant.
- CNS acting medications will be reviewed for likelihood of seizure risk according to purpose for which the medication was prescribed, dose, speed of dose change (increase or decrease), combination with other CNS active drugs or other factors potentially contributing to lower the seizure threshold (i.e., sleep deprivation, alcohol consumption, marijuana therapeutic and recreational use).
- The determination (by clinical and/or scientific subject matter experts) of likely or plausible seizure risk will be used to make these decisions:

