  - To optimize patient safety and mitigate risk, participant should be titrated off a specific medication(s) or receive a lower dose or alternate medication during study participation:
    - If clinical experts determine that the medication(s) can be safely withdrawn or changed, then participant remains eligible.
    - If clinical experts determine that the medication(s) cannot be safely withdrawn or changed, then the participant will be excluded.

To optimize patient safety and mitigate risk, participant should remain on medication as prescribed and remains eligible for study participation.

For Veterans remaining eligible, medical records will be further reviewed to document biological sex, age, time post ischemic stroke or TBI onset and current co-morbid medical conditions. Dictated radiology reports, as well as other records, will be reviewed to document right vs left cortical and sub cortical ischemic strokes and number of ischemic strokes. Radiology reports as well as clinical notes (e.g., History and Physical) will be reviewed to delineate TBI by etiology including diffuse axonal injury (DAI) and  $\geq 1$  contusion (e.g., blast, vehicular, assaults) or DAI +  $\geq 1$  contusion + an anoxic event subsequent to TBI (e.g., respiratory, cardiac). These variables will be examined for use as covariates in analyses.

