Persons who do not have AUD or SUD but do consume alcohol and/or use illicit substances at a level, as determined by clinical and/or scientific experts (e.g., Research Neuropsychiatrist [name], Neuropsychologist [name], Neurologist/Epileptologist [name]) and/or scientific subject matter expert (e.g., [name]), likely to elevate seizure risk (i.e., hazardous level plausibly lowering of seizure threshold) will be excluded.

If a participant screens positive on the AUDIT-C (Men score of 4 or more, women score of 3 or more), then they will be referred to their clinical care team for further evaluation and clinical management.

If a participant scores 1 to 2 on the DAST, then substance use will be monitored by having researchers re-administer the DAST on each study day.

[figure not shown]
If at any time a participant scores a 3 or more on the DAST, then they will be referred to their clinical care team for further evaluation and clinical management.

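### The iTBS pause, stop and reschedule rules contain no hold for a new or changed non-stimulant CNS drug given for a non-psychiatric reason, or for alcohol, marijuana or other substance use, although entry screens these for seizure risk

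*Combined protocol and SAP*

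**What the plan says.** **At entry.** Section 5.1 (Screening Medical Records, Medication Review) sends all CNS-acting drugs to clinical or scientific experts and deliberately avoids a fixed drug list. The factors weighed include "speed of dose change (increase or decrease), combination with other CNS active drugs", together with sleep, alcohol and marijuana: "or other factors potentially contributing to lower the seizure threshold (i.e., sleep deprivation, alcohol consumption, marijuana therapeutic and recreational use". The timing is stated: prescribed and self-reported drugs, alcohol and "substance use (DAST-10) will be evaluated prior to enrollment". One possible outcome is that the "participant should be titrated off a specific medication(s) or receive a lower dose or alternate medication during study participation"; another is that the drug continues as prescribed. Under In-Person Eligibility Confirmation, people without a use disorder whose alcohol or illicit substance use is judged "likely to elevate seizure risk (i.e., hazardous level plausibly lowering of seizure threshold) will be excluded".

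**On study.** For those scoring 1 to 2 on the DAST, "substance use will be monitored by having researchers re-administer the DAST on each study day". "If at any time a participant scores a 3 or more on the DAST, then they will be referred to their clinical care team", with no mention of iTBS. The AUDIT-C is scheduled only at Study-Day 0.

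**The session rules.** Protection Against Risk introduces three lists: five pause rules, five stop rules and two reschedule rules. Stop rule 3 and reschedule rule 1 concern CNS stimulants. Stop rule 4 opens with any change to prescribed drugs but then narrows to "either initiating a new mental health medication or experiencing a prescribed change in dose for mental health reasons during study participation". Reschedule rule 2 lets the epileptologists postpone a session after disrupted sleep.

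**The concern.** The plan treats sleep loss, alcohol, marijuana, drug combinations and dose changes as parts of one seizure-risk judgement at entry. Only some of them carry over to the day of stimulation. Staff have a written route to postpone a session after a bad night. They have none for a drug newly started for pain or spasm, a return to heavier drinking, or a DAST that has risen to 3.

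What is at stake is participant safety. No estimate or test is affected. Potential Risks names seizure as the main worry with TMS, and the text after the reschedule rules says that the risk in brain injury or ischemic stroke is unknown and that iTBS might provoke one. Entry does not remove these factors: some participants stay on CNS drugs, non-hazardous drinkers are not excluded, and Table 3 lists medical and recreational marijuana use as covariate levels. Followed as written, the rules would let a session proceed after a change that would have gone to expert review at entry.

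**Working it through.** The plan gives no figure on this point, so the check sets the entry factors beside the session rules and then looks for a hold placed elsewhere.

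**1. Count of rules.** 5 pause + 5 stop + 2 reschedule = 12. Drug rules: stop 3, stop 4, reschedule 1 = 3. Sleep: reschedule 2 = 1. The remaining 12 − 3 − 1 = 8 concern seizure (two rules), scalp breakdown, headache, suicidality, visuomotor speed, shock and pregnancy.

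**2. Entry factor against session rule.**

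| Factor | Session rule on study |
|---|---|
| CNS stimulants | Stop 3, reschedule 1 |
| Mental-health drug started, or dose changed for that reason | Stop 4 |
| Sleep deprivation | Reschedule 2 |
| Other CNS-acting drug started or changed for another reason | None |
| Return to a non-stimulant, non-psychiatric drug withdrawn or lowered for seizure risk | None |
| Alcohol | None; AUDIT-C at Day 0 only |
| Marijuana | None; recorded as a covariate |
| Other non-stimulant substances | None; repeat DAST for scores of 1 to 2, referral at 3 or more |

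**3. A hold elsewhere?** Protection Against Risk tracks 12 indicators each study day (blood pressure, heart rate, fatigue, tinnitus, sleep, dizziness, nausea, vomiting, confusion, seizure, headache, neck pain). None asks about drugs, alcohol or substances. The visit lists for Study-Days 2, 3 and 5 contain no such enquiry. Stop rules 3 and 4 imply that someone asks about medication, but no time or form is given. The Table 2 battery has no marijuana or alcohol item. A participant scoring 0 on the DAST at entry has no scheduled repeat.

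**4. Time for status to change.** From the visit headings, counting from Study-Day 1: Day 2 is at 4 days; Day 3 at 4 + 14 = 18; Day 4 at 18 + 14 = 32; Day 5 falls within two weeks of Day 4, so at 32 to 46. The gap from Day 0 to Day 1 is not stated, so 4, 18 and 32 days are minimum ages for the AUDIT-C at the three sessions.

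**5. Sessions a new rule would cover.** At most 48 + 48 + 12 = 108, of which 24 + 24 + 12 = 60 are active. This is the reach of the rule, not a count of sessions at risk.

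**6. Where a check must sit.** On Days 2 and 3 the PE battery precedes iTBS. Table 2 gives 1.0 h (neuropsychological tests) + 1.5 h (AMPS) + 6 × 0.1 h (mood, agitation and fatigue) = 3.1 h. A hold called after that could mean repeating B0 or B2 and using another of the 11 AMPS tasks, which are never reused for the same Veteran.

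**The case against.** The best defence is that the window is short and the cohort is chosen for stability. The CDW screen excludes drug or dose changes within three months of list extraction, Table 1 excludes medication changes within three months of starting, and the records review confirms three months of medical stability. The two main sessions then follow within weeks. Section 5.7 lets the PI withdraw a participant for health or safety reasons, or for non-compliance, which would reach someone who returns to a drug the experts had withdrawn. The daily indicators carry specified medical responses by severity, so acute drug or alcohol effects might surface as confusion, dizziness or altered vital signs. The Data Safety Monitoring Scale and the IDE safety protocols are cited but not reproduced and could already ask the question.

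Most of this stands, and it makes the point small. It does not close the gap. Stability before entry says nothing about a change after it; withdrawal under 5.7 is discretionary and is not a temporary hold; and no visible text tells staff to ask.

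A reader might go further and infer that participants are stimulated without seizure protection, or that many of the 108 sessions are unsafe. The documents do not support either. There is a baseline EEG read by epileptologists, exclusion for recent seizure and for anti-epileptic treatment of seizures, stimulation at 80% of resting motor threshold, treatment in a Rapid Response area and a timed seizure plan. Placebo sessions deliver no stimulation. Nor does the marijuana covariate show that use changes on study; it shows only that existing users are expected.

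**Conclusion.** The concern holds as a minor safety improvement. As written, 0 of the 12 session rules cover a new or changed non-stimulant CNS drug given for a non-psychiatric reason, or alcohol, marijuana or other non-stimulant substance use, and an on-study DAST of 3 or more has no stated consequence for iTBS. This is narrower than the plan's own entry review.

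The conclusion rests on two readings. The final clause of stop rule 4 is taken to limit the rule, and the exclusion for hazardous use is taken as an eligibility criterion because it appears under eligibility screening. It also rests on the visible text; the two unreproduced safety documents could shrink the gap to a missing cross-reference and a missing hold. The documents give no frequency for such changes, so neither affected sessions nor seizures can be estimated. No aim, estimate or analysis is affected.

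**What to change.** **Ask.** At the start of Study-Days 2 and 3, before the PE battery (or by telephone the day before), and before iTBS on optional Day 5, ask every participant in both arms one question. Since the entry review or the last session, have they started, stopped or changed the dose of any CNS-acting drug, or newly started or increased alcohol, marijuana or other substance use? Where a repeat DAST is already due, give it at the same time.

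**Hold.** Add a third reschedule rule. If the answer is yes, or a DAST of 3 or more has not been reviewed, the epileptologist or another of the existing experts decides before that day's testing (on Day 5, before iTBS) whether to proceed, delay or withdraw.

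**Leave alone.** Stop rule 4 stays unchanged. No drug list, cut-off or extra AUDIT-C or DAST is needed. If the Data Safety Monitoring Scale or the IDE protocol already asks this, cite it and add only the hold.

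**Cost.** Assuming 1 to 2 minutes per check, 108 × 1 = 108 min (1.8 h) to 108 × 2 = 216 min (3.6 h) over the trial, or 1/480 = 0.2% to 2/480 = 0.4% of an 8-hour visit. Asking both arms protects the blind. Expert time for positive answers and rebooking come on top and cannot be costed without a rate. A delayed visit would stretch the two-week interval for that Veteran. The question relies on self-report from people with memory problems, as the existing stimulant and sleep rules do.
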